Appendix 1. Abbreviations

The following is a list of abbreviations that may be used in the protocol.

Abbreviation	Term
Ab	anti-body
ABCP	atezolizumab plus BCP
AChR	acetylcholine receptor
ACRIN	American College of Radiology Imaging Network
ADA	anti-drug antibodies
AdC68	a chimpanzee adenovirus 68
AE	adverse event
AIDS	acquired immunodeficiency syndrome
ALK WT	Anaplastic lymphoma kinase wild-type
ALT	alanine aminotransferase
ANC	absolute neutrophil count
ANOVA	analysis of variance
ART	antiretroviral therapy
ASCO	American Society of Clinical Oncology
AST	aspartate aminotransferase
AUC	area under the curve
AUC _{inf}	area under the curve plasma concentration versus time curve from time 0 extrapolated to infinity
AUC _{last}	area under the curve plasma concentration following the first dose from time 0 to last time point
CCI	[REDACTED]
BCP	bevacizumab plus carboplatin plus paclitaxel
BCT	blood collection tube
BID	twice daily
BP	blood pressure
BRAF	proto-oncogene protein B-raf
BSA	body surface area
BUN	blood urea nitrogen
C	Cycle
CAR	chimeric antigen receptor
CBR	clinical benefit rate
CL/F	apparent serum clearance
C _{max}	maximum plasma concentration
C1D1	cycle 1 day 1
CHF	congestive heart failure
cHL	classical Hodgkin lymphoma
ChTx	chemotherapy treatment
CI	confidence interval

Abbreviation	Term
CISH	chromogenic in situ hybridization
CK	creatine kinase
CL	Clearance
CLL	chronic lymphocytic leukemia
CNS	central nervous system
COVID-19	coronavirus disease of 2019
CR	complete response
CRF	case report form
CRM	Continual Reassessment Method
CSA	clinical study agreement
CSF	cerebrospinal fluid
CSR	clinical study report
CT	computed tomography
CT	clinical trial
CTA	clinical trial application
CCI	[REDACTED]
CTCAE	Common Terminology Criteria for Adverse Events
CTLA4	Anti-cytotoxic T Lymphocyte-associated antigen 4
cTnI	cardiac troponin-I
CV	coefficient of variation
DILI	drug-induced liver injury
DLI	donor lymphocyte infusion
DLT	dose-limiting toxicity
DMC	data monitoring committee
DNA	deoxyribonucleic acid
DR	duration of Response
DU	dispensable unit
D/U	dose de-escalation
DOR	duration of response
DOSD	duration of stable disease
EC	ethics committee
ECC	emergency contact card
ECG	Electrocardiogram
ECOG	Eastern Cooperative Oncology Group
E-DMC	external data monitoring committee
EDP	exposure during pregnancy
EDTA	ethylenediaminetetraacetic acid
EFS	event-free survival
Eg	for example
EGFR	epidermal growth factor receptor
EI	equivalence interval

Abbreviation	Term
EML4	echinoderm microtubule-associated protein-like 4
EP	evaluable population
ER	estrogen receptor
Etc	‘and other things’ or ‘and so forth’
EU	European Union
EudraCT	European Clinical Trials Database
FDA	Food and Drug Administration (United States)
FFPE	formalin-fixed paraffin-embedded
FIP	first in patient
FISH	fluorescence in situ hybridization
FSH	follicle-stimulating hormone
GCP	Good Clinical Practice
GGT	gamma-glutamyl transferase
GI	gastrointestinal
GnRH	gonadotropin-releasing hormone agonist
GPI	glycophosphatidylinositol
GVAX	cancer vaccine
GVHD	graft versus host disease
HBV	hepatitis B virus
HCC	hepatocellular carcinoma
HCV	hepatitis C virus
HER2	human epidermal growth factor 2
Hgb	Hemoglobin
HIV	human immunodeficiency virus
HR	heart rate / hazard ratio
IB	investigator’s brochure
ICH	International Conference on Harmonisation
ICOS	inducible T-cell costimulatory
ID	Identification
Ie	that is
IFN	Interferon
Ig	Immunoglobulin
IgG4	immunoglobulin G4
IHC	immunohistochemistry
IM	intramuscular
IP	investigational product
IND	investigational new drug application
INR	international normalized ratio
IP manual	Investigational Product manual
IRB	institutional review board
IRC	internal review committee

Abbreviation	Term
irCR	immune related – complete response
irPD	immune related – progressive disease
irPR	immune related – partial response
irSD	immune related – stable disease
IRT	interactive response technology
ISR	injection site reaction
IUD	intrauterine device
IV	intravenous
IWR	interactive Web-based response
CCI	[REDACTED]
kDa	kilodalton
KRAS	proto-oncogene
LAG3	lymphocyte activation gene 3
LDH	lactate dehydrogenase
LFT	liver function test
LM	listeria monocytogene
LSLV	last subject last visit
LVEF	left ventricular ejection fraction
mAb	monoclonal antibody
MCC	Merkel cell carcinoma
MD	multiple dose
MedDRA	Medical Dictionary for Regulatory Activities
MFD	maximum feasible dose
MG	myasthenia gravis
MHC	major histocompatibility complex
mITT	modified intend to treat
mNSCLC	metastatic non-small cell lung cancer
mOS	median overall survival
MPF	megakaryocyte potentiating factor
mPFS	median progression-free survival
MRI	magnetic resonance imaging
MSLN	mesothelin
MTD	maximum tolerated dose
mTNBC	metastatic triple negative breast cancer
mTPI	modified toxicity probability interval
mTTP	median time to progression
MUC1	mucin 1, cell surface associated
N/A	not applicable
NAb	neutralizing antibody
NCI	National Cancer Institute

Abbreviation	Term
NCI CTCAE	National Cancer Institute Common Terminology Criteria for Adverse Events
NHPs	nonhuman primates
NK	natural killer
NSCLC	non-small cell lung cancer
OBD	optimal biological dose
OR	Objective Response or Overall Response
ORR	objective response rate
OS	overall survival
CCI	[REDACTED]
PCD	primary completion date
PD	pharmacodynamics
PD	progressive disease
PD-1	programmed death – 1
PD-L1	programmed death – ligand 1
pDNA	Plasmid deoxyribonucleic acid
PET	positron emission tomography
PFS	Progression-Free Survival
PFS	prefilled syringe
PI	principal investigator
PK	Pharmacokinetic
PGx	pharmacogenomics
PP	per protocol
PR	partial response
PR	progesterone receptor
PrCa	prostate cancer
PrCaVBIR	Prostate Cancer Vaccine-based Immunotherapy Regimen
PS	performance status
PSA	Prostate specific antigen
PSCA	Prostate stem cell antigen
PSMA	Prostate specific membrane antigen
pT	Target probability
PT	prothrombin time
PTT	partial thromboplastin time
QD	every day
QT	time between the start of the Q wave and the end of the T wave
QTcF	QT interval with Fridericia's correction
QxW	Every x# of Weeks, ie, Q2W, Q4W, Q6W, Q12W)
RCC	renal cell carcinoma
RD	Response/Remission Duration
RECIST	Response Evaluation Criteria in Solid Tumors

Abbreviation	Term
RET	rearranged during transfection
RFS	Relapse-Free Survival
CCI	[REDACTED]
ROS1	ROS proto-oncogene 1, receptor tyrosine kinase
RP2D	recommended Phase 2 dose
RR	response rate
SAE	serious adverse event
SAP	statistical analysis plan
SARS-CoV2	severe acute respiratory syndrome coronavirus 2
SC	Subcutaneous
SCCHN	squamous cell carcinoma of the head and neck
SCLC	small cell lung cancer
SD	single dose / stable disease
SGOT	serum glutamic-oxaloacetic transaminase
SGPT	serum glutamic-pyruvic transaminase
SOA	Schedule of Activities
SOP	standard operating procedure
SRSD	single reference safety document
T _{1/2}	terminal elimination half-life
T _{max}	time to maximum plasma concentration
Tbili	total bilirubin
TAAs	tumor associated antigens
TBR	tumor background ratio
CCI	[REDACTED]
TERT	telomerase reverse transcriptase
TILs	tumor infiltrating lymphocytes
TKIs	tyrosine kinase inhibitors
TDS-IM	(Ichor) Intramuscular TriGrid Delivery System
TNBC	triple negative breast cancer
TRAEs	treatment-related adverse events
TRK	tyrosine receptor kinase
TSH	thyroid stimulating hormone
TTP	time to progression
ULN	upper limit of normal
UPM	unit probability mass
US	United States
USPI	United States Package Insert
UVB	ultraviolet B
VBIR-2	Vaccine-based immunotherapy regimen - 2
VP	viral particles
Vz/F	volume of distribution

Abbreviation	Term
WBC	white blood cell
WHO	World Health Organization
WT	wild-type

Appendix 2. ECOG Performance Status

Grade	ECOG Performance Status
0	Fully active, able to carry on all pre-disease performance without restriction.
1	Restricted in physically strenuous activity but ambulatory and able to carry out work of a light or sedentary nature, eg, light house work, office work.
2	Ambulatory and capable of all self-care but unable to carry out any work activities. Up and about more than 50% of waking hours.
3	Capable of only limited self-care, confined to bed or chair more than 50% of waking hours.
4	Completely disabled. Cannot carry on any self-care. Totally confined to bed or chair.
5	Dead.

*As published in Am J Clin Oncol 5:649 655, 1982

Appendix 3. RECIST (Response Evaluation Criteria In Solid Tumors) version 1.1 Guidelines

Adapted from E.A. Eisenhauer, et al: New response evaluation criteria in solid tumours: Revised RECIST guideline (version 1.1). European Journal of Cancer 45 (2009) 228–247.

CATEGORIZING LESIONS AT BASELINE

Measurable Lesions

Lesions that can be accurately measured in at least one dimension.

- Lesions with longest diameter twice the slice thickness and at least 10 mm or greater when assessed by CT or MRI (slice thickness 5-8 mm).
- Lesions with longest diameter at least 20 mm when assessed by Chest X-ray.
- Superficial lesions with longest diameter 10 mm or greater when assessed by caliper.
- Malignant lymph nodes with the short axis 15 mm or greater when assessed by CT.

NOTE: The shortest axis is used as the diameter for malignant lymph nodes, longest axis for all other measurable lesions.

Non-measurable disease

Non-measurable disease includes lesions too small to be considered measurable (including nodes with short axis between 10 and 14.9 mm) and truly non-measurable disease such as pleural or pericardial effusions, ascites, inflammatory breast disease, leptomeningeal disease, lymphangitic involvement of skin or lung, clinical lesions that cannot be accurately measured with calipers, abdominal masses identified by physical exam that are not measurable by reproducible imaging techniques.

- Bone disease: Bone disease is non-measurable with the exception of soft tissue components that can be evaluated by CT or MRI and meet the definition of measurability at baseline.
- Previous local treatment: A previously irradiated lesion (or lesion subjected to other local treatment) is non-measurable unless it has progressed since completion of treatment.

Normal sites

- Cystic lesions: Simple cysts should not be considered as malignant lesions and should not be recorded either as target or non-target disease. Cystic lesions thought to represent cystic metastases can be measurable lesions, if they meet the specific definition above. If non-cystic lesions are also present, these are preferred as target lesions.

- Normal nodes: Nodes with short axis <10 mm are considered normal and should not be recorded or followed either as measurable or non-measurable disease.

Recording Tumor Assessments

All sites of disease must be assessed at baseline. Baseline assessments should be done as close as possible prior to study start. For an adequate baseline assessment, all required scans must be done within 28 days prior to treatment and all disease must be documented appropriately. If baseline assessment is inadequate, subsequent statuses generally should be indeterminate.

Target lesions

All measurable lesions up to a maximum of 2 lesions per organ, 5 lesions in total, representative of all involved organs, should be identified as target lesions at baseline. Target lesions should be selected on the basis of size (longest lesions) and suitability for accurate repeated measurements. Record the longest diameter for each lesion, except in the case of pathological lymph nodes for which the short axis should be recorded. The sum of the diameters (longest for non-nodal lesions, short axis for nodal lesions) for all target lesions at baseline will be the basis for comparison to assessments performed on study.

- If two target lesions coalesce the measurement of the coalesced mass is used. If a large target lesion splits, the sum of the parts is used.
- Measurements for target lesions that become small should continue to be recorded. If a target lesion becomes too small to measure, 0 mm should be recorded if the lesion is considered to have disappeared; otherwise a default value of 5 mm should be recorded.

NOTE: When nodal lesions decrease to <10 mm (normal), the actual measurement should still be recorded.

Non-target disease

All non-measurable disease is non-target. All measurable lesions not identified as target lesions are also included as non-target disease. Measurements are not required but rather assessments will be expressed as ABSENT, INDETERMINATE, PRESENT/NOT INCREASED, INCREASED. Multiple non-target lesions in one organ may be recorded as a single item on the case report form (eg, 'multiple enlarged pelvic lymph nodes' or 'multiple liver metastases').

OBJECTIVE RESPONSE STATUS AT EACH EVALUATION

Disease sites must be assessed using the same technique as baseline, including consistent administration of contrast and timing of scanning. If a change needs to be made the case must be discussed with the radiologist to determine if substitution is possible. If not, subsequent objective statuses are indeterminate.

Target disease

- Complete Response (CR): Complete disappearance of all target lesions with the exception of nodal disease. All target nodes must decrease to normal size (short axis <10 mm). All target lesions must be assessed.
- Partial Response (PR): Greater than or equal to 30% decrease under baseline of the sum of diameters of all target measurable lesions. The short diameter is used in the sum for target nodes, while the longest diameter is used in the sum for all other target lesions. All target lesions must be assessed.
- Stable: Does not qualify for CR, PR or Progression. All target lesions must be assessed. Stable can follow PR only in the rare case that the sum increases by less than 20% from the nadir, but enough that a previously documented 30% decrease no longer holds.
- Objective Progression (PD): 20% increase in the sum of diameters of target measurable lesions above the smallest sum observed (over baseline if no decrease in the sum is observed during therapy), with a minimum absolute increase of 5 mm.
- Indeterminate. Progression has not been documented, and
 - one or more target measurable lesions have not been assessed;
 - or assessment methods used were inconsistent with those used at baseline;
 - or one or more target lesions cannot be measured accurately (eg, poorly visible unless due to being too small to measure);
 - or one or more target lesions were excised or irradiated and have not reappeared or increased.

Non-target disease

- CR: Disappearance of all non-target lesions and normalization of tumor marker levels. All lymph nodes must be 'normal' in size (<10 mm short axis).
- Non-CR/Non-PD: Persistence of any non-target lesions and/or tumor marker level above the normal limits.

- PD: Unequivocal progression of pre-existing lesions. Generally the overall tumor burden must increase sufficiently to merit discontinuation of therapy. In the presence of stable disease (SD) or PR in target disease, progression due to unequivocal increase in non-target disease should be rare.
- Indeterminate: Progression has not been determined and one or more non-target sites were not assessed or assessment methods were inconsistent with those used at baseline.

New Lesions

The appearance of any new unequivocal malignant lesion indicates PD. If a new lesion is equivocal, for example due to its small size, continued assessment will clarify the etiology. If repeat assessments confirm the lesion, then progression should be recorded on the date of the initial assessment. A lesion identified in an area not previously scanned will be considered a new lesion.

Supplemental Investigations

- If CR determination depends on a residual lesion that decreased in size but did not disappear completely, it is recommended the residual lesion be investigated with biopsy or fine needle aspirate. If no disease is identified, objective status is CR.
- If progression determination depends on a lesion with an increase possibly due to necrosis, the lesion may be investigated with biopsy or fine needle aspirate to clarify status.

Subjective progression

Participants requiring discontinuation of treatment without objective evidence of disease progression should not be reported as PD on tumor assessment CRFs. This should be indicated on the end of treatment CRF as off treatment due to Global Deterioration of Health Status. Every effort should be made to document objective progression even after discontinuation of treatment.

Table 17. Objective Response Status at each Evaluation

Target Lesions	Non-target Disease	New Lesions	Objective status
CR	CR	No	CR
CR	Non-CR/Non-PD	No	PR
CR	Indeterminate or Missing	No	PR
PR	Non-CR/Non-PD, Indeterminate, or Missing	No	PR
SD	Non-CR/Non-PD, Indeterminate, or Missing	No	Stable
Indeterminate or Missing	Non-PD	No	Indeterminate
PD	Any	Yes or No	PD
Any	PD	Yes or No	PD
Any	Any	Yes	PD

Table 18. Objective Response Status at each Evaluation for Participants with Non-Target Disease Only

Non-target Disease	New Lesions	Objective status
CR	No	CR
Non-CR/Non-PD	No	Non-CR/Non-PD
Indeterminate	No	Indeterminate
Unequivocal progression	Yes or No	PD
Any	Yes	PD

Appendix 4. National Cancer Institute (NCI) Common Terminology Criteria for Adverse Events (CTCAE)

The NCI CTCAE (Version 5.0 dated November 27, 2017) has been placed in the Study Manual for this protocol. Alternatively, the NCI CTCAE may be reviewed on-line at the following NCI website:

https://ctep.cancer.gov/protocoldevelopment/electronic_applications/ctc.htm

Appendix 5. Management of Immune-related Adverse Events (irAEs)

Management of irAEs including Myasthenia Gravis		
Gastrointestinal irAEs		
Severity of Diarrhea/Colitis (NCI-CTCAE v5.0)	Initial Management	Follow-up Management
Grade 1 Diarrhea: <4 stools/day over Baseline Colitis: asymptomatic	-Continue study treatment. -Symptomatic treatment (eg, loperamide).	-Close monitoring for worsening symptoms. -Educate patient to report worsening immediately. -If worsens: Treat as Grade 2, 3 or 4.
Grade 2 Diarrhea: 4 to 6 stools per day over Baseline; IV fluids indicated <24 hours; not interfering with ADL Colitis: abdominal pain; blood in stool	-Withhold study treatment. -Symptomatic treatment.	-If improves to Grade ≤ 1 : Resume study treatment. -If persists >5-7 days or recurs: Treat as Grade 3 or 4.
Grade 3 to 4 Diarrhea (Grade 3): ≥ 7 stools per day over Baseline; incontinence; IV fluids ≥ 24 h; interfering with ADL Colitis (Grade 3): severe abdominal pain, medical intervention indicated, peritoneal signs Grade 4: life-threatening, perforation	-Withhold for Grade 3. -Permanently discontinue study treatment for Grade 4 or recurrent Grade 3. -1.0 to 2.0 mg/kg/day prednisone IV or equivalent. -Add prophylactic antibiotics for opportunistic infections. -Consider lower endoscopy.	-If improves: -Continue steroids until Grade ≤ 1 , then taper over at least 1 month; resume study treatment following steroids taper (for initial Grade 3). -If worsens, persists >3 to 5 days, or recurs after improvement: -Add infliximab 5mg/kg (if no contraindication). -Note: infliximab should not be used in cases of perforation or sepsis.

Dermatological irAEs		
Grade of Rash (NCI-CTCAE v5.0)	Initial Management	Follow-up Management
Grade 1 to 2 Covering \leq 30% body surface area	
 -Continue study treatment. -Symptomatic therapy (for example, antihistamines, topical steroids). 	
 -If persists >1 to 2 weeks or recurs: 
 -Withhold study treatment; -Consider skin biopsy. -Consider 0.5-1.0 mg/kg/day prednisone or equivalent. Once improving, taper steroids over at least 1 month, consider prophylactic antibiotics for opportunistic infections, and resume study treatment following steroids taper. -If worsens: Treat as Grade 3 to 4.
Grade 3 to 4 Grade 3: Covering $>30\%$ body surface area; Grade 4: Life threatening consequences	
 -Withhold study treatment for Grade 3. -Permanently discontinue for Grade 4 or recurrent Grade 3. -Consider skin biopsy. -Dermatology consult. -1.0 to 2.0 mg/kg/day prednisone or equivalent. -Add prophylactic antibiotics for opportunistic infections. 	
 -If improves to Grade ≤ 1: -Taper steroids over at least 1 month; resume study treatment following steroids taper (for initial Grade 3).

Pulmonary irAEs		
Grade of Pneumonitis (NCI-CTCAE v5.0)	Initial Management	Follow-up Management
Grade 1 Radiographic changes only	
 -Consider withholding study treatment. -Monitor for symptoms every 2 to 3 days. -Consider Pulmonary and Infectious Disease consults. 	
 -Re-assess at least every 3 weeks. -If worsens: Treat as Grade 2 or Grade 3 to 4.
Grade 2 Mild to moderate new symptoms	
 -Withhold study treatment. -Pulmonary and Infectious Disease consults. -Monitor symptoms daily; consider hospitalization. -1.0 to 2.0 mg/kg/day prednisone or equivalent. -Add prophylactic antibiotics for opportunistic infections. -Consider bronchoscopy, lung biopsy. 	
 -Re-assess every 1 to 3 days If improves: -When symptoms return to Grade ≤ 1, taper steroids over at least 1 month, and then resume study treatment following steroids taper. -If not improving after 2 weeks or worsening: Treat as Grade 3 to 4.
Grade 3 to 4 Grade 3: Severe new symptoms; New/worsening hypoxia; Grade 4: Life-threatening	
 -Permanently discontinue study treatment. -Hospitalize. -Pulmonary and Infectious Disease consults. -1.0 to 2.0 mg/kg/day prednisone or equivalent. -Add prophylactic antibiotics for opportunistic infections. -Consider bronchoscopy, lung biopsy. 	
 If improves to Grade ≤ 1: -Taper steroids over at least 1 month. -If not improving after 48 hours or worsening: Add additional immunosuppression (for example, infliximab, cyclophosphamide, IV, -immunoglobulin, or mycophenolate mofetil).

Hepatic irAEs		
Grade of Liver Test Elevation (NCI-CTCAE v5.0)	Initial Management	Follow-up Management
Grade 1 Grade 1 AST or ALT > ULN to 3.0 x ULN and/or Total bilirubin > ULN to 1.5 x ULN	-Continue study treatment.	-Continue liver function monitoring. -If worsens: Treat as Grade 2 or 3 - 4.
Grade 2 AST or ALT >3.0 to \leq 5 x ULN and/or total bilirubin >1.5 to \leq 3 x ULN	-Withhold study treatment. -Increase frequency of monitoring to every 3 days.	-If returns to Grade \leq 1: -Resume routine monitoring; resume study treatment. -If elevation persists >5 to 7 days or worsens: -Treat as Grade 3 to 4.
Grade 3 to 4 AST or ALT >5 x ULN and/or total bilirubin >3 x ULN	-Permanently discontinue study treatment. -Increase frequency of monitoring to every 1 to 2 days. -1.0 to 2.0 mg/kg/day prednisone or equivalent. -Add prophylactic antibiotics for opportunistic infections. -Consult gastroenterologist/hepatologist. -Consider obtaining MRI/CT scan of liver and liver biopsy if clinically warranted.	-If returns to Grade \leq 1: -Taper steroids over at least 1 month. -If does not improve in >3 to 5 days, worsens or rebounds: -Add mycophenolate mofetil 1 gram (g) twice daily. -If no response within an additional 3 to 5 days, consider other immunosuppressants per local guidelines.

Renal irAEs		
Grade of Creatinine Increased (NCI-CTCAE v5.0)	Initial Management	Follow-up Management
Grade 1 Creatinine increased > ULN to 1.5 x ULN	-Continue study treatment.	-Continue renal function monitoring -If worsens: Treat as Grade 2 to 3 or 4.
Grade 2 to 3 Creatinine increased >1.5 and ≤6 x ULN	-Withhold study treatment. -Increase frequency of monitoring to every 3 days. -1.0 to 2.0 mg/kg/day prednisone or equivalent. -Add prophylactic antibiotics for opportunistic infections. -Consider renal biopsy.	-If returns to Grade ≤ 1 : -Taper steroids over at least 1 month, and resume study treatment following steroids taper. -If worsens: -Treat as Grade 4.
Grade 4 Creatinine increased >6 x ULN	-Permanently discontinue study treatment. -Monitor creatinine daily. -1.0 to 2.0 mg/kg/day prednisone or equivalent. -Add prophylactic antibiotics for opportunistic infections Consider renal biopsy. -Nephrology consult.	-If returns to Grade ≤ 1 : Taper steroids over at least 1 month.

[figure not shown]
Cardiac irAEs		
Myocarditis	Initial Management	Follow-up Management
New onset of cardiac signs or symptoms and / or new laboratory cardiac biomarker elevations (eg, troponin, CK-MB, BNP) or cardiac imaging abnormalities suggestive of myocarditis.	
 -Withhold study treatment. -Hospitalize. -In the presence of life threatening cardiac decompensation, consider transfer to a facility experienced in advanced heart failure and arrhythmia management. -Consult cardiologist to establish etiology and rule-out immune-mediated myocarditis. -Guideline based supportive treatment as per cardiology consult.* -Consider myocardial biopsy if recommended per cardiology consult. 	
 -If symptoms improve and immune-mediated etiology is ruled out, restart study treatment. -If symptoms do not improve/worsen, viral myocarditis is excluded, and immune-mediated etiology is suspected or confirmed following cardiology consult, manage as immune-mediated myocarditis.
Immune-mediated myocarditis.	
 -Permanently discontinue study treatment. -Guideline based supportive treatment as appropriate as per cardiology consult.* 1.0 to 2.0 mg/kg/day prednisone or equivalent. -Add prophylactic antibiotics for opportunistic infections. 	
Once improving, taper steroids over at least 1 month.
 
If no improvement or worsening, consider additional immunosuppressants (eg, azathioprine, cyclosporine A).

*Local guidelines, or eg. ESC or AHA guidelines

ESC guidelines website: <https://www.escardio.org/Guidelines/Clinical-Practice-Guidelines> AHA guidelines website:

http://professional.heart.org/professional/GuidelinesStatements/UCM_316885_Guidelines-Statements.jsp.

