Non-hematologic	Continue at the same dose level.	For pneumonitis, endocrinopathy, colitis, creatinine, AST, ALT, or total bilirubin elevations, withhold dose until toxicity is Grade ≤ 1 , or has returned to baseline, then resume at the same dose level or reduce by 1 level (considering each compound separately) at the discretion of the investigator. For all other events, continue at the same dose level.	For pneumonitis, colitis, endocrinopathy, creatinine, AST, ALT or total bilirubin elevations, or pruritus discontinue treatment.** For all other events withhold dose until toxicity is Grade ≤ 1 , or has returned to baseline, then resume treatment at the same dose level or reduce the dose by 1 level (considering each compound separately) at the discretion of the investigator.* Treatment may resume with VBIR-2 with an interruption of sasanlimab for one dose at the discretion of the investigator.	Discontinue treatment.**
Hematologic	Continue at the same dose level.	Continue at the same dose level.	Withhold dose until toxicity is Grade ≤ 2 , or has returned to baseline, then resume treatment at the same dose level.	Discontinue treatment.**

* Nausea, vomiting, or diarrhea must persist at Grade 3 despite maximal medical therapy to require dose modification.

** For Grade ≥ 3 colitis or pneumonitis, discontinue treatment permanently. For any grade of myocarditis discontinue treatment permanently. For all other conditions participants may be allowed to remain in the study to receive the VBIR-2 2 after the toxicity is Grade ≤ 1 or returned to baseline, and only if agreed upon by the Investigator and Sponsor.

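### For four steroid-treated immune-related events, Table 12 lets checkpoint inhibitors restart on toxicity grade alone while Appendix 5 requires a completed taper of at least 1 month, and no sentence says which governs

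*Protocol*

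**What the plan says.** **Section 5.4.2** lists what must be met before re-treatment: neutrophils, platelets, and non-hematologic toxicity back to baseline or Grade ≤1. The investigator may accept Grade ≤2 if it is not a safety risk. Steroids are not mentioned.

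**Table 12 (Section 5.4.5.3)** covers toxicity related to sasanlimab and/or tremelimumab.
- Grade 2 pneumonitis and creatinine elevation: withhold until Grade ≤1 or baseline, "then resume at the same dose level or reduce by 1 level".
- Other Grade 2 events, which include rash: "For all other events, continue at the same dose level".
- Grade 3 events outside its named list, which include rash and diarrhea without colitis: withhold until Grade ≤1 or baseline, "then resume treatment at the same dose level or reduce the dose by 1 level (considering each compound separately"). A footnote adds that diarrhea must persist at Grade 3 despite maximal therapy before any dose modification.

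**Appendix 5** gives prednisone 1.0 to 2.0 mg/kg/day for the four events and places restart after the taper.
- Grade 2 pneumonitis: "taper steroids over at least 1 month, and then resume study treatment following steroids taper".
- Initial Grade 3 diarrhea: steroids until Grade ≤1, "then taper over at least 1 month; resume study treatment following steroids taper (for initial Grade 3").
- Initial Grade 3 rash, after a taper of at least 1 month: "resume study treatment following steroids taper (for initial Grade 3").
- Grade 2 to 3 creatinine: "Taper steroids over at least 1 month, and resume study treatment following steroids taper".
- Grade 1 to 2 rash that persists more than 1 to 2 weeks or recurs: withhold and consider prednisone at 0.5 to 1.0 mg/kg/day. "Once improving, taper steroids over at least 1 month, consider prophylactic antibiotics for opportunistic infections, and resume study treatment following steroids taper".

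Sections 5.4.5.2 and 5.4.5.3 both point to Appendix 5. Section 5.4.5.3 introduces Table 12 as general rules from which action may differ after evaluation by the investigator and the sponsor. Only Table 6, for AdC68, expressly sets immune-related events aside to Appendix 5.

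**The concern.** A site that reads Table 12 and Section 5.4.2 at the point of dosing finds nothing about steroids. It could re-expose a participant to two checkpoint inhibitors partway through the taper, when the Grade ≤1 that permits restart is a grade observed on prednisone. A site that reads Appendix 5 would wait. The same event could then be rechallenged differently across sites, and safety and tolerability are a primary objective of Part 2 (Section 2.2).

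**Working it through.** No statistical figure in the plan is at issue. The check sets the texts side by side and then counts days.

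**Step 1. Where the texts differ**

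| Event | Table 12 | Appendix 5 |
|---|---|---|
| Grade 2 pneumonitis | Restart at Grade ≤1 or baseline | Restart after taper of at least 1 month |
| Grade 2 creatinine | Same | Same |
| Initial Grade 3 rash | Same | Same |
| Initial Grade 3 diarrhea, no colitis | Same, if modification is required at all | Same |
| Grade 2 rash persisting >1 to 2 weeks | Continue dosing | Withhold; if steroids are given, taper first |
| Grade 3 colitis | Discontinue permanently | Restart after taper (initial Grade 3) |
| Grade 3 creatinine | Discontinue; return only if investigator and sponsor agree | Restart after taper |

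Appendix 5 is stricter in the first five rows and Table 12 in the last two, so neither text can simply be ranked above the other. Grade 2 colitis or liver events that resolve promptly need no steroids under Appendix 5, and there the texts agree.

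**Step 2. Is there a tie-break?** The general-rules sentence does not name Appendix 5. The pointers say only that algorithms exist. Section 5.7.7 limits chronic palliative or supportive corticosteroids but sets no restart condition.

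**Step 3. Size in days.** For the four events the Appendix 5 taper starts at Grade ≤1, the point at which Table 12 already permits restart. The earliest permitted restarts are therefore at least 1 month apart. The maintenance schedule defines a month as 28 days; Appendix 5 does not define it.

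Let r be the days from the last dose to Grade ≤1, with 28-day dosing and a 28-day taper:
- Table 12 dose day = max(28, r)
- Appendix 5 dose day = r + 28
- Delay = r + 28 − max(28, r) = min(r, 28)

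| r | Table 12 day | Appendix 5 day | Delay (days) |
|---|---|---|---|
| 7 | 28 | 35 | 7 |
| 14 | 28 | 42 | 14 |
| 21 | 28 | 49 | 21 |
| 28 | 28 | 56 | 28 |
| 35 | 35 | 63 | 28 |

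A longer taper lengthens every delay. The dose moves, because treatment-period visit windows follow the previous dosing visit; none is necessarily lost.

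**Step 4. Illustration of steroid dose.** Assume a linear 28-day taper to zero from day r. Prednisone on the Table 12 dose day is then start × min(r, 28)/28. Body weights are assumed.

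| Start dose | r = 7 | r = 14 | r = 21 | r at which 10 mg is reached (280/start) |
|---|---|---|---|---|
| 50 mg (50 kg × 1.0) | 12.5 | 25 | 37.5 | 5.6 days |
| 70 mg (70 kg × 1.0) | 17.5 | 35 | 52.5 | 4.0 days |
| 140 mg (70 kg × 2.0) | 35 | 70 | 105 | 2.0 days |
| 180 mg (90 kg × 2.0) | 45 | 90 | 135 | 1.6 days |

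The 10 mg yardstick is the daily dose that Part 2 exclusion criterion 10 calls immunosuppressive. It is an entry criterion, not an on-study rule.

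**Step 5. Collision with the discontinuation prompts.** The text following the Section 5.4.2 list (printed under the run-on heading 5.4.3) allows resumption after more than 2 weeks of interruption only with obvious clinical benefit and sponsor agreement. Section 5.4.5.3 prompts sasanlimab discontinuation after more than 4 weeks. Counted from the missed dose, the Step 3 delay exceeds 14 days whenever r > 14. Counted from the start of withholding, time to recovery plus 28 days exceeds both limits. Appendix 5 thus already sits awkwardly with these prompts, and adding the taper to Section 5.4.2 without addressing them would push participants toward stopping.

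**The case against.** The best defence is that a specific rule overrides a general one. Table 12 covers any related toxicity, and Appendix 5 covers the immune-related subset. The protocol points to Appendix 5 and labels Table 12 general. The Section 5.4.2 list states necessary conditions and is not a licence to ignore the appendix. A site that re-doses during the taper breaches Appendix 5, so it is not compliant with the protocol as a whole.

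Much of this stands. The evident intent for the four events is that the taper be completed, and a careful site would do so. Three things remain. The general-rules sentence leaves departures to case-by-case evaluation. Specific-over-general would loosen Grade 3 colitis from permanent discontinuation to restart. And for persistent Grade 2 rash a site cannot literally satisfy both texts, since one says continue and the other says withhold.

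A reader might also infer that Table 12 permits the vaccine during high-dose steroids. The documents do not support that for the Grade 2 events: that cell does not mention the vaccine, and Table 6 defers immune-related events to Appendix 5 for AdC68. VBIR-2 appears only in Table 12's Grade 3 cell and in the ** footnote, which requires investigator and sponsor agreement. The point is therefore confined to the two checkpoint inhibitors.

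It is also fair that the list of events has soft edges. For persistent rash Appendix 5 only says to consider prednisone, and Grade 2 colitis lasting more than 5 to 7 days is escalated to Grade 3 or 4 management. A rule based on steroid treatment handles these better than a fixed list.

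**Conclusion.** The inconsistency is real and should be fixed: two stated dosing rules disagree for the four events, and also for persistent Grade 2 rash. The gap in earliest permitted restart is at least 28 days, which is a floor. The shift in the actual dose is min(r, 28) days under 28-day dosing and a 28-day taper. The prednisone figures are illustrations that rest on assumed weights and a linear taper.

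Three stronger conclusions are not supported. Appendix 5 cannot be declared to prevail everywhere, because Table 12 is stricter for Grade 3 colitis and Grade 3 creatinine. No number of affected participants can be given, because the documents report no incidence for these events. And nothing here shows an effect on the clinical benefit rate.

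**What to change.** Add one sentence to Section 5.4.2 and repeat it as a Table 12 footnote: *For irAEs treated with systemic steroids where restart is permitted, restart only when the event is Grade ≤1 (or baseline) and the Appendix 5 steroid taper is completed; where Table 12 and Appendix 5 differ, the stricter applies, and the Table 12 discontinuation rules and ** footnote are unchanged.*

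Do not copy the unqualified Table 6 parenthesis into Table 12. It would hand Grade 3 colitis and Grade 3 creatinine to Appendix 5, which allows restart where Table 12 discontinues.

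State as well that time spent completing an Appendix 5 taper after recovery to Grade ≤1 does not by itself count toward the two-week or four-week discontinuation prompts. Otherwise a taper of at least 1 month would routinely trigger the obvious-clinical-benefit test.

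The cost is a few lines in a clarification letter or the next amendment, with no added visits, data or participants. The downside is that affected participants restart later than Table 12 alone would allow, by the delays in the working, and by more if the taper runs longer than 28 days.
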